11.2.1. Study Participant Disposition

A subject disposition flow diagram will be prepared that will summarize the disposition of all subjects entered into the study, including the number of subjects entered and enrolled into the study, and the number who received at least 1 dose of study treatment. Subjects who discontinued from the study will be summarized by their reasons.

11.2.2. Study Participant Characteristics

Demographic and baseline information will be summarized using descriptive statistics. For continuous variables, the mean, standard deviation (SD), median, minimum, and maximum will be presented. For categorical variables, the number of subjects, frequency, and percentages will be presented. Individual subject demographics and baseline information will be presented in data listings.

Concomitant therapy used during the study period will be listed and summarized by dose group.

11.2.3. Treatment Compliance

Compliance will be ensured for administration of LY3202328 in Part A and administration of LY3202328, simvastatin and atorvastatin in Part B, as study drug will be administered at the CRU under the supervision of the investigator.

Treatment compliance for LY3202328 in Part B will be ensured on days of subject confinement to the CRU and study visits, but will be assessed by comparing returned pills with dispensed pills (the percentage of the actual number of capsules taken versus the number of capsules expected to be taken) for dosing days while not confined to the CRU.

Subjects who demonstrated significant noncompliance (<80% or >120% of the intended dose taken in a visit interval) will also be summarized.

Study medication administration data and deviation(s) from the prescribed dosage regimen should be recorded in the subject's CRF.

11.3. Statistical Analyses

Statistical analysis of this study will be the responsibility of Chorus or its designee.

Pharmacokinetic/PD and safety analyses will be conducted on the PK and Safety populations, respectively.

Additional exploratory analyses of the data will be conducted as deemed appropriate. Study results may be pooled with the results of other studies for population PK analysis purposes to avoid issues with post-hoc analyses and incomplete disclosures of analyses.

11.3.1. Safety Analyses

11.3.1.1. Clinical Evaluation of Safety

All LY3202328 and protocol procedure AEs will be listed, and, if the frequency of events allows, safety data will be summarized using descriptive methodology.

The incidence of symptoms for each treatment will be presented by severity and by association with investigational product as perceived by the investigator. Symptoms reported to occur prior to study entry will be distinguished from those reported as new or increased in severity during the study. Each symptom will be classified by the most suitable term from the current medical regulatory dictionary. Severity of the AE will be assessed according to the "Toxicity Grading Scale for Healthy Adult and Adolescent Volunteers Enrolled in Preventive Vaccine Clinical Trials 2007".

The number of investigational product-related SAEs will be reported.

11.3.1.2. Statistical Evaluation of Safety

The primary endpoint of this study is the number and severity of treatment-emergent adverse events (TEAEs), clinical laboratory abnormalities, changes in vital sign measurements, and other safety endpoints after administration of LY3202328 or placebo. Summary statistics will be provided by dose group and for all study subjects combined wherever appropriate. For

continuous variables, summary statistics will include number of subjects, mean, median, SD, minimum, and maximum. Categorical endpoints will be summarized using number of subjects, frequency, and percentages. Additional analysis will be performed if warranted upon review of the data.

11.3.2. Pharmacokinetic Analyses

Pharmacokinetic parameter estimates for LY3202328, simvastatin (Part B only), and atorvastatin (Part B only) in plasma will be calculated by standard noncompartmental methods of analysis.

The primary PK parameters for analysis will be C_{max} and AUC. The primary AUC metric will be calculated AUC from time zero to infinity ($AUC_{0-\infty}$) on Day 1 (Parts A and B) and AUC during one dosing interval (AUC_{0-t}) on Day 28 of Part B of LY3202328 after single- and multiple-dose administrations (Parts A and B, respectively). If the half-life ($t_{1/2}$) was relatively long, $AUC_{0-\infty}$ may not be calculable for Day 1 of Part B, and would thus not be reported.

Other noncompartmental parameters, such as T_{max} , $t_{1/2}$, trough concentration (C_{trough}), apparent clearance (CL/F), and apparent volume of distribution (V/F) may be reported. Descriptive statistics of PK parameters will be presented with each dose.

Renal clearance of LY3202328 will be calculated as the ratio of amount excreted in urine/AUC. This will be compared to the unbound glomerular filtration rate, which is estimated using creatinine.

Pharmacokinetic parameter estimates (C_{max} and AUC) for LY3202328 will be evaluated to delineate effects of dose proportionality using a power model approach (Smith et al. 2000).

Drug-drug interaction assessment of the effect of LY3202328 coadministration on simvastatin and atorvastatin exposure will be conducted using ANOVA. Pharmacokinetic parameter estimates (C_{max} and AUC) for simvastatin and atorvastatin administered alone or coadministered with LY3202328 will be compared. The ratios of statin exposure with and without LY3202328 coadministration at different dose levels of LY3202328 will be estimated, along with their confidence intervals.

The impact of food on the rate and extent of absorption of LY3202328 will be assessed by estimating the ratio of C_{max} and $AUC_{0-\infty}$ in the fed and fasted state of at the same dose level. The ratio will be calculated within each subject, and then summarized for the group. Similarly, the difference in T_{max} between the fed and fasted will be calculated and summarized.

Other analyses, including PK modeling, may be conducted on the PK data.

11.3.3. Pharmacodynamic and Biomarker Analyses

The PD assessments conducted in this study are typical and appropriate for a Phase I single and multiple ascending dose evaluations of a novel therapeutic agent. The TG concentrations will be analyzed to evaluate evidence of target engagement and intended pharmacological benefits.

Visual and tabular summarization of all PD measurements will be done. For the endpoints in the primary or secondary objectives, a statistical analysis will also be conducted.

Mixed effect model repeated measure will be the default method of analysis for PD endpoints with time-course data. For endpoints with only baseline and end-of-therapy measurements, ANCOVA will be the default, with baseline as a covariate. Other covariates may be a priori defined and included in the model.

Normality assumption will be tested using an appropriate visual or statistical method, and, if it is violated, log transformation may also be performed on these data. The most sensitive analysis will be selected to test the effect of LY3202328 on the change from baseline in these PD data.

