The primary PK parameters for analysis will be maximum plasma concentration (C_{max}) and area under the plasma concentration-time curve (AUC) for LY3202328. The primary AUC metric will be calculated AUC from time zero to infinity ($AUC_{0-\infty}$) after single dose administration and AUC during one dosing interval (AUC_{0-t}) on day 28 after multiple dose administration. Pharmacokinetic parameter estimates (C_{max} and AUC) for LY3202328 will be evaluated to delineate effects of dose proportionality using a power model approach.

Drug-drug interaction assessment of the effect of LY3202328 coadministration on simvastatin and atorvastatin exposure will be conducted using ANOVA. Pharmacokinetic parameter estimates (C_{max} and AUC) for simvastatin and atorvastatin, administered alone or coadministered with LY3202328, will be compared. The ratios of statin exposure with and without LY3202328 coadministration at different dose levels of LY3202328 will be estimated, along with their confidence intervals.

The impact of food on the rate and extent of LY3202328 absorption will be assessed by calculating and summarizing the ratios of C_{max} and $AUC_{0-\infty}$, as well as the difference in the time to reach C_{max} (T_{max}), with and without food at the same dose level.

Review of PK may occur during the conduct of Part A and B to confirm exposure trends.

Pharmacodynamics

The PD assessments conducted in this study are typical and appropriate for Phase I single and multiple ascending dose evaluations of a novel therapeutic agent. The triglycerides concentrations will be analyzed to evaluate evidence of target engagement and intended pharmacological benefits.

Visual and tabular summarization of all PD measurements will be done. For the endpoints in the primary or secondary objectives, a statistical analysis will also be conducted.

Mixed effect model repeated measure would be the default method of analysis for PD endpoints with time-course data. For endpoints with only baseline and end-of-therapy measurements, ANCOVA will be the default, with baseline as a covariate. Other covariates may be a priori defined and included in the model.

Normality assumption will be tested using an appropriate visual or statistical method and, if it is violated, log transformation may also be performed on these data. The most sensitive analysis will be selected to test the effect of LY3202328 on the change from baseline in these PD data.

4. Introduction

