7.1. Inclusion Criteria

Subjects are eligible for inclusion in the study only if they meet all of the following criteria at screening and/or enrollment:

- [1] are healthy males or females, as determined by medical history and physical examination
 - male subjects:
 - agree to use a reliable method of birth control during the study and 3 months following the last dose of the investigational product. Acceptable methods of birth control may include: 1) condom with spermicide; 2) Diaphragm with spermicide; or 3) female condom with spermicide.
 - female subjects:
 - postmenopausal women include women with either:
 - spontaneous amenorrhea for at least 12 months, not induced by a medical condition such as anorexia nervosa and not taking medications that induced amenorrhea (for example: oral contraceptives, hormones, gonadotropin releasing hormone, anti-estrogens, selective estrogen receptor modulators, or chemotherapy; or
 - spontaneous amenorrhea for 6 to 12 months and a follicle-stimulating hormone (FSH) level greater than 40 mIU/mL; or
 - women with a prior history of hysterectomy or bilateral oophorectomy have to be at least 40 year of age and FSH >40 mIU/mL.
- [2] are at least 18 to 70 years old inclusive (for males), or 40 to 70 years old, inclusive (for females), at the time of study entry.
- [3] are on a stable diet and exercise regimen for >3 months prior to screening.
- [4] have a BMI of 25.0 – 35.0 (Part A) or 27.0 – 40.0 kg/m² (Part B) , inclusive, at screening.
- [5] have a fasting TG between 150 and 499 mg/dL, inclusive, at screening (allowed but not required in Part A; required for Part B only).
- [6] have a fasting LDL-c between 100 and 200 mg/dL inclusive, at screening (allowed but not required in Part A; required for Part B only).

- [7] have clinical laboratory test results within normal reference range for the population or investigator site, or results with acceptable deviations that are judged to be not clinically significant by the investigator. However, aspartate aminotransferase (AST), alanine aminotransferase (ALT), gamma-glutamyl transpeptidase (GGT), and alkaline phosphatase (ALP) have to be $\leq 1.5 \times$ upper limit of normal (ULN); total bilirubin has to be within normal limit, unless in subjects with Gilbert's Syndrome; thyroid stimulating hormone (TSH) $< \text{ULN}$.
- [8] estimated glomerular filtration rate $\geq 60 \text{ mL/minute/1.73m}^2$ with no proteinuria (defined as 1+ or greater on urine dipstick).

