analysis may be used if warranted. In some cases, nonparametric analysis may be the initially proposed method due to the expected distribution of response. Whenever alternative methods of analysis are required, the description of the new method along with the rationale for its use will be documented in the CSR.

The eCRF data for all subjects will be provided in Standard Data Tabulation Model (SDTM) datasets, and the production of the tables, figures and listings for the study will be generated from the SDTM datasets. Data listings supplied as part of the CSR will be sorted by investigative site and subject identification number, and subjects will be identified in the listings by the investigator number concatenated with the subject number.

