All PD analyses will be performed using the PD population. Presentations of PD analyses will include the number of subjects with data at each time point plus related statistics derived from the analysis. Subjects who received Placebo during more than 1 dosing period in Part A will have their data from different dosing periods reported separately. The following sections contain the planned analyses. If plots of the raw data or residuals suggest alternative analysis techniques, such as log-transformation or nonparametric methods, then additional analyses will also be performed. The rationale for and results of the alternatives techniques will be described in the CSR.

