6.1.2 Fasting Lipid Profile Analyses in Part B

Fasting lipid profiles will be collected from all subjects in Part B just prior to dosing on the day of dosing, Day 7, Day 14, Day 21, and Day 28, and 7 (Day 35) days after stopping dosing of the randomized treatment. An additional follow-up assessment will be collected 14 (Day42) or 28 (Day 56) days after stopping dosing of the randomized treatment for Cohort 3 (5mg QD) and Cohorts 4 through 6, respectively.

A last on-treatment observation measurement will be derived for each subject using the last post-dose measurement for a lipid parameter taken while the subject is taking study medication during the 28-day treatment period. Change from baseline for each of the lipid parameters will be derived for each of the post-dosing time points (Days 7, 14, 21, 28, 35, and 42 or 56) and the last on-treatment observation using the pre-dose measurement from the first day of dosing as the baseline.

Descriptive statistics for the measurement at baseline and the measurement and change from baseline at each post-baseline time point plus the last observation will be tabulated.

An MMRM analysis will be conducted for each lipid parameter using the change from baseline values from Days 7, 14, 21, 28, 35, and 42. The MMRM model for change from baseline will contain fixed effects for treatment, time, and their interaction, a random effect for subject, and the baseline measurement as a covariate. Since the time points are evenly spaced the covariance structure among the repeated measurements for a subject will be assumed to be common across subjects and modeled using a autoregressive(1) 7x7 matrix. Satterthwaite's approximation will be used to estimate denominator degrees of freedom. Any missing assessments will be assumed to be missing at random, so estimates of treatment effects from the model will be unbiased.

These analyses will be performed using the SAS procedure PROC MIXED. The tabular output for these MMRM analyses will present the least squares means, standard errors and 95% confidence intervals and Type 3 p-values for each main effect marginal. Pairwise contrasts of the least squares means between the LY dose levels and placebo along with the associated 95% confidence interval and Type 3 p-values will also be provided at each time point using LSMESTIMATE statements.

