Plots of the least squares mean \pm standard error estimates for each lipid parameter over time (baseline through Day 56) will be provided by treatment group.

A last on-treatment observation analysis will be performed for change from baseline using an analysis of covariance (ANCOVA) model with a fixed effect for treatment a random effect for subject and the baseline value as a covariate. Tabular output for these ANCOVA analyses will present the least squares means, standard errors and 95% confidence intervals and Type 3 p-values for each main effect marginal. Pairwise contrasts of the least squares means between each

LY dose level and placebo along with the associated 95% confidence interval and Type 3 p-values will also be provided.

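### The protocol selects the most sensitive PD analysis, which modestly inflates nominal type I error and is not withdrawn by the SAP; one model and scale should be fixed in advance

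*Protocol*

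**What the plan says.** **Protocol.** Section 11.3.3 makes MMRM the default for time-course PD endpoints and ANCOVA the default where there are only two measurements. Normality is to be checked by an unnamed visual or statistical method, and "if it is violated, log transformation may also be performed on these data". Then comes the selection rule: "The most sensitive analysis will be selected to test the effect of LY3202328 on the change from baseline in these PD data". The synopsis carries the same rule ("The most sensitive analysis will be selected"). Neither place says what sensitive means or which result carries the conclusion.

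**SAP.** Section 6.1.2 (fasting lipids, Part B) plans untransformed models for all lipids, triglycerides (TG) included: "An MMRM analysis will be conducted for each lipid parameter using the change from baseline values". It adds: "A last on-treatment observation analysis will be performed for change from baseline using an analysis of covariance (ANCOVA) model". The two are not ranked. Section 6 provides for further analyses "If plots of the raw data or residuals suggest alternative analysis techniques, such as log-transformation or nonparametric methods"; these are run in addition to the planned ones. Section 2 says: "Whenever alternative methods of analysis are required, the description of the new method along with the rationale for its use will be documented in the" study report. The selection rule does not appear in the SAP, and nothing there says that it no longer applies.

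**Context.** Fasting lipids are a secondary objective, TG is the named marker of target engagement (Protocol 11.3.3), and the sample size is not based on hypothesis testing (Protocol 11.1). SAP 2.5 marks multiplicity adjustment as not applicable.

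**The concern.** A rule that selects the test by its sensitivity, after the data have been inspected, reads most naturally as selection on the result. The p-value of a selected test is smaller than its nominal level justifies. The SAP plans a p-value and a 95% confidence interval for each dose against placebo at each time point. Protocol 10.6 looks for at least one dose with evidence of target engagement, and the data are meant to inform later doses.

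The selection could also be made with treatment known. Under Protocol 11.3.4, unblinded sponsor staff review Part B lipids after the 20, 100 and 300 mg levels. SAP 2.1 allows all sponsor personnel to be unblinded to a cohort once its dosing is complete.

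A second question is which scale to fix for TG. Part B subjects must "have a fasting TG between 150 and 499 mg/dL", a 499/150 = 3.3-fold range. Preclinical effects are quoted in percent (Protocol 4 and 6.5), which makes a proportional effect plausible without establishing it in humans.

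**Working it through.** The documents give no alpha, effect size or SD for PD endpoints, so there is no figure of the plan to reproduce.

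**Inputs from the documents.** Four cohorts of 8 active and 2 placebo (Protocol 6.1.2). With the five SAP 2.2.2 treatment groups this is 8 per dose against 4 × 2 = 8 pooled placebo. Screening TG is 150–499 mg/dL.

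**Assumptions.** Two-sided 5% per contrast, inferred from the 95% intervals. Log-normal TG, median 220 mg/dL, between-subject log SD 0.30. Within-subject CV 20–40%, with log SD = √ln(1 + CV²), for example √ln(1.04) = 0.198 at 20%. No dropout. Most sensitive is read as smallest p-value. The model is a Day 28 ANCOVA on all 40 subjects with baseline as covariate and pooled error, df = 40 − 6 = 34. It stands in for the MMRM.

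**1. Type I error per contrast (%), top dose v placebo, 6,000 runs, simulation SE about 0.3 points**

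| Rule | CV 20% | CV 30% | CV 40% |
|---|---|---|---|
| Raw fixed | 5.4 | 5.1 | 5.4 |
| Log fixed | 5.3 | 5.2 | 5.3 |
| Log tried only after a failed Shapiro-Wilk test, then smaller p | 5.8 | 5.9 | 6.4 |
| Smaller p of raw and log | 6.6 | 6.4 | 6.8 |
| Smallest p of raw, log and rank | 7.8 | 7.8 | 8.4 |

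A rerun at CV 25–35% gave 5–6% for the gated rule and 6–7% for the free raw/log choice. For two independent tests the figure would be 1 − 0.95² = 9.75%. Raw and log results are highly correlated, so the inflation is far smaller.

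With the scale fixed, the chance of at least one false positive over four doses is still 15.5–16%. That is the separate multiplicity issue.

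**2. Raw against log for TG, same layout**

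| Assumed true effect | Quantity | CV | Raw | Log |
|---|---|---|---|---|
| 30% fall at every dose | power | 20% | 80% | 77% |
| | | 30% | 53% | 49% |
| | | 40% | 38% | 35% |
| 35% fall at top dose only | power, top dose | 20% | 80% | 90% |
| | | 25% | 63% | 78% |
| | | 30% | 50% | 66% |
| | | 40% | 33% | 47% |
| Falls of 0/20/35/50% | false positive, lowest dose | 20–40% | 10–11% | 5.0–5.6% |

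**3. Hand check of the last row.** If a fall of fraction e shrinks the raw-scale SD by (1 − e), the relative variances in placebo and the four doses are 1, 1, 0.64, 0.4225 and 0.25. Their mean is 3.3125/5 = 0.6625. The inert-dose contrast is then divided by a standard error that is too small by √0.6625 = 0.814. The critical value 2.03 acts like 2.03 × 0.814 = 1.65, whose two-sided tail on 34 df is about 11%. This ignores the covariate but agrees with the simulation. On the log scale the spread is equal across groups and the error stays near 5%.

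**The case against.** The strongest reply is that the SAP already settles this. Section 1.1 says that it describes the procedures to be used, Section 2.3 assigns PD endpoints to MMRM, and Section 6.1.2 fixes outcome, covariate and contrasts. Alternatives are prompted by plots, not by the treatment p-value, and are reported alongside the planned result. On that view the protocol sentence is stale wording. Much of this stands: it keeps the problem small if the SAP governs. But neither document says that the SAP replaces the protocol's rule, and the SAP does not rank its MMRM against its ANCOVA.

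Three stronger readings are tempting, and the documents do not support them:

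- **That type I error reaches 9.5–12.5%.** Such figures need choices the protocol's rule does not name: percent change, an unadjusted t test, or a Day 7–28 mean. The only alternative named beside the rule is log transformation after a normality failure. Even the 8% figure borrows rank methods from SAP Section 6, where they are additional, not selected.
- **That the p-values have no validity at all.** A shift from 5% to 6–7% does not justify this in a study without a formal alpha.
- **That the SAP's raw scale is an error that always loses power.** Raw holds its type I error when no dose works, and it is slightly more powerful when all doses act equally. A comparison of 8 v 8 subjects in isolation favours log, but the SAP fits all five groups together.

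**Conclusion.** The point holds in a limited form. The selection rule stands in two places in the protocol and is not withdrawn. Followed as written, it makes nominal p-values somewhat too small: about 5–6% if log is tried only after a failed normality test, 6–7% for a free raw/log choice, and about 8% with a rank test eligible. These sizes rest on log-normal TG, CV 20–40% and the smallest-p reading. If sensitive was meant in some harmless sense, the text does not say so. What is affected is the nominal p-values and the target-engagement conclusion, not a confirmatory claim.

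Fixing log for TG is a sound preference, conditional on effects being proportional and differing by dose. Under that assumption the raw model's pooled error doubles the false-positive rate for an inert lowest dose. It also costs 10–16 points of power, typically about 15, when only the top dose works. The sizes come from an ANCOVA. The planned MMRM also assumes a covariance common to all subjects, so the mechanism carries over, but the exact figures may differ.

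**What to change.** 1. Delete the selection sentence in Protocol 11.3.3 and in the synopsis.
2. State that the SAP's MMRM is the planned analysis for fasting lipids. Label the last on-treatment ANCOVA, and any other scale or rank method, as sensitivity analyses.
3. Name the scale for each lipid before unblinding. Given Protocol 11.3.4 and SAP 2.1, that means before the first Part B cohort is unblinded to sponsor staff.
4. For TG, prefer change in log(TG) with log baseline as covariate, back-transformed to percent change against placebo.

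**Cost.** Wording only; no subject, visit or sample changes. TG results would be reported as ratios instead of mg/dL, and power would be about 3–4 points lower if all doses had equal effect. The sponsor gives up the freedom to choose among results. Multiplicity over doses, lipids and time points is not solved by this and needs its own statement.
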